#### **12.4.3 Criteria**

#### **12.4.4 Data Monitoring Committee**

No data monitoring committee will be established in this study.

### **12.5 Sample Size Determination**

Each cohort: 6 or 12 subjects for the DS-1040b group in the 0.6 mg cohort

16 subjects each for the 1.2, 2.4, and 4.8 mg cohort (12 and 4 subjects in the DS-1040b and placebo groups, respectively)

Total: 54 or 60 subjects

#### **<Rationale>**

The sample size in each cohort (6 or 12 subjects in each DS-1040b group) and the study discontinuation criterion (occurrence of two events of symptomatic intracranial hemorrhage [defined by ECASS] in the DS-1040b group in one cohort) were selected in reference to Study DS1040-A-U103, which is ongoing in Europe and the United States, to confirm the safety and tolerability of DS-1040b monotherapy in patients with acute ischemic stroke. The sample size for Study DS1040-A-U103 was determined based on the results of clinical studies of rt-PA therapy. Based on the 16% incidence of symptomatic intracranial hemorrhage in these clinical studies of rt-PA therapy, a sample size that allows the assessment of an incidence of symptomatic intracranial hemorrhage of  $\leq$  16% (16 subjects per cohort) and the criterion for proceeding to the next cohort (occurrence of two events of symptomatic intracranial hemorrhage [defined by ECASS] in the DS-1040b group in one cohort) were selected in Study DS1040-A-U103.

In the 0.6 mg cohort, the safety in 6 or 12 subjects in the DS-1040b group will be confirmed. If DS-1040b at this dose is shown to be safe, the study will proceed to the next cohort.

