In a drug-drug interaction study with clopidogrel (DS1040-A-E106) conducted in the United Kingdom, the safety and tolerability of DS-1040b given as a single intravenous dose after 6 days of clopidogrel treatment in 22 healthy (non-Japanese) subjects were evaluated. Each subject received a loading dose of 300 mg clopidogrel in the morning of Day 1, followed by a daily dose of 75 mg clopidogrel on Days 2 to 6. In the morning of Day 6, the daily dose of clopidogrel was followed immediately by a 12-hour intravenous infusion of DS-1040b 20 mg. Compared with pretreatment baseline, prolongation of the mean bleeding time (Surgicutt method) was observed with clopidogrel given until Day 5. Plasma DS-1040a concentration parameters after coadministration of DS-1040b and clopidogrel were 290 ng/mL and 3670 h·ng/mL for Cmax and AUC, respectively, and no prolongation of the mean bleeding time was observed. A single intravenous dose of DS-1040b after 6 days of clopidogrel treatment was safe and well-tolerated, and no safety concerns were detected.

In an ethnic differences study (DS1040-A-E108) conducted in the United Kingdom, Caucasian, Japanese, Chinese, and Korean subjects (12 subjects each) received a 12-hour intravenous infusion of DS-1040b 20 mg. No ethnic differences in pharmacokinetic parameters were observed. Safety and tolerability were also confirmed in Japanese, Chinese, and Korean subjects.

Currently, Studies DS1040-A-U103 in patients with acute ischemic stroke (ClinicalTrials.gov identifier NCT02586233) and DS1040-B-U107 (NCT02923115) in patients with acute pulmonary embolism are ongoing in the Europe and the United States.

Study DS1040-A-U103, which is ongoing in the United States, the United Kingdom, Germany, and France, is a safety and tolerability study in patients within 4.5 hours to 12 hours after the onset of ischemic stroke. It is an intergroup ascending dose study using a total of 6 cohorts, and DS-1040b is administered intravenously over 6 hours at 6 doses: 0.6, 1.2, 2.4, 4.8, 7.2, and 9.6 mg. Sixteen subjects are enrolled in each cohort (8 or 16 subjects for Cohorts 1 and 2), and are randomized to a DS-1040b or placebo group in a 3:1 ratio. As of Feb 2017, 9 subjects (7 subjects in the United States and 2 subjects in

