It is also expected that the recurrence of acute ischemic stroke immediately after treatment of the disease may be prevented if the study confirms a persistent effect of continuous treatment with DS-1040b on fibrinolytic biomarkers (sustained inhibition of TAFIa activity and increase in the blood D-dimer level). Therefore, fibrinolytic biomarkers will be assessed as a secondary endpoint in this study.

The results of the recently reported HERMES study show that the incidence of symptomatic intracranial hemorrhage in patients receiving standard drug treatment and patients also receiving thrombectomy device treatment was 4.3% and 4.4%, respectively, indicating a similar rate of bleeding between these two groups of patients. The results of the Rescue-Japan registry show that the incidence of symptomatic intracranial hemorrhage in patients receiving rt-PA therapy combined with endovascular treatment was 7.0% and 3.1% in patients with ICA occlusion and patients with MCA M1 region occlusion, respectively, compared with 4.9% and 3.1%, respectively, among those receiving endovascular treatment alone. These study results suggest that the incidence of symptomatic intracranial hemorrhage is similar between patients receiving standard drug treatment, standard drug treatment in combination with a thrombectomy device, and thrombectomy device treatment alone. It is unlikely that DS-1040b, which is expected to have a lower bleeding risk than existing fibrinolysis activators, will increase the incidence of symptomatic intracranial hemorrhage when used in combination with a thrombectomy device.

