Study DS1040-A-U103, which is ongoing in Europe and the United States, is a study intended to confirm the safety and tolerability of DS-1040b in patients within 4.5 hours to 12 hours after the onset of ischemic stroke. Patients in whom standard treatment (rt-PA therapy and thrombectomy device treatment) is indicated, are excluded. There are 6 cohorts in total, and 16 subjects (8 or 16 subjects in Cohorts 1 and 2) are enrolled in each cohort. The sample size was selected based on the results of clinical studies of the standard drug treatment of rt-PA therapy. Based on the 16% incidence of symptomatic intracranial hemorrhage in these clinical studies of rt-PA therapy, a sample size that allows the assessment of an incidence of symptomatic intracranial hemorrhage of <= 16% (8 or 16 subjects per cohort, a total of 80 to 96 subjects in all 6 cohorts combined) and the criterion for proceeding to the next cohort (occurrence of two events

of symptomatic intracranial hemorrhage in the DS-1040b group in one cohort) were selected in Study DS1040-A-U103. Since the incidence of symptomatic intracranial hemorrhage in the present study enrolling patients undergoing thrombectomy device treatment alone is expected to be similar to that observed in patients included in Study DS1040-A-U103, it was considered appropriate to use the same sample size for each cohort in the present study as in Study DS1040-A-U103.

The results of the DAWN (2017) and DEFUSE3 (2018) studies confirmed that thrombectomy device treatment can be safely achieved up to 24 hours after the onset of ischemic stroke by selecting appropriate patients based on the imaging findings. With the aim of confirming the safety in patients treated with thrombectomy device treatment, which is expected to show a rapid increase in the number of target patients in the future, this study involves patients in principle within 8 hours after the onset of ischemic stroke, the range indicated in the package insert of the thrombectomy device in Japan.

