### 3. STUDY DESIGN

#### 3.1 Overall Design

This study is a multicenter, single-blind, placebo-controlled, randomized, intergroup ascending dose study to confirm the safety and tolerability of DS-1040b in patients with acute ischemic stroke in whom a thrombectomy device is indicated. There will be a total of 4 cohorts, with a planned sample size of 54 or 60 subjects (6 or 12 subjects in the 0.6 mg cohort and 16 subjects per cohort in the other cohorts). The 0.6 mg cohort will only consist of a DS-1040b group. In the other cohorts, subjects will be randomized to the DS-1040b or placebo group in a 3:1 ratio. If any one of the first 6 subjects in the 0.6 mg cohort experiences one event defined as one requiring, “necessary actions to be taken, including discontinuation of the study” as specified in Section 12.4.2, an additional 6 subjects will be enrolled to confirm the safety in a total of 12 subjects. In each cohort, subjects will be evaluated one by one to confirm the absence of symptomatic intracranial hemorrhage through Visit 2 (36 hours after study drug administration) before enrolling the next subject, until 3 subjects aged  $\geq 81$  years are enrolled in the DS-1040b group. In each cohort, safety evaluation will be performed when all data collected through Visit 4 (96 hours after study drug administration) are available to determine whether the study should proceed to the next cohort. Subjects will be required to receive inpatient treatment until Visit 4 at the earliest.

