#### **12.4.2 Criteria for Discontinuation or Temporary Discontinuation of the Study**

If any of the criteria specified below are met, the study will be discontinued or temporarily discontinued. Similarly, the study may be discontinued or temporarily discontinued according to these criteria until 3 subjects aged  $\geq 81$  years are enrolled in the DS-1040b group in each cohort.

- 1) If the criterion below is met, the study will be discontinued at that point. After the decision on discontinuation is made, the sponsor will discontinue the study according to the procedures described in Section 16.9:
  - Occurrence of two events of symptomatic intracranial hemorrhage (intracranial hemorrhage with clinical deterioration causing an increase in the NIISS score of  $\geq 4$  points [defined by ECASS]) not attributable to external factors at 36 hours after the start of DS-1040b administration in the DS-1040b group in one cohort
- 2) To ensure the safety of subjects, subject enrollment will be temporarily discontinued and the necessary actions to be taken, including discontinuation of the study, will be considered if any of the criteria listed below are met. If the study is continued based on the results of consideration, subject enrollment will be resumed. If the study is discontinued, the sponsor will discontinue the study according to the procedures described in Section 16.9:
  - Occurrence of one event of symptomatic intracranial hemorrhage (intracranial hemorrhage with clinical deterioration causing an increase in the NIHSS score of  $\geq 4$  points [defined by ECASS]) not attributable to external factors at 96 hours after the start of study drug administration (Visit 4) in the DS-1040b group in one cohort
  - Occurrence of one event of non-intracranial (TIMI) major bleeding at 96 hours after the start of study drug administration (Visit 4) in the DS-1040b group in one cohort
  - Occurrence of any events requiring the consideration of study discontinuation, such as severe hepatic impairment (eg, total bilirubin  $\geq 10$  mg/dL, AST or ALT  $\geq 500$  IU/L, ALP of 5 times the study center’s reference range, bleeding tendency, symptoms of hepatic failure, including consciousness disorder [fulminant hepatitis], hepatic cirrhosis, hepatic tumor, jaundice persisting for

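### Does the cohort-size rationale have to say what 12 treated subjects per dose can show about a 16% rate of symptomatic intracranial hemorrhage?

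*Combined protocol and SAP*

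**What the plan says.** Protocol 12.5 plans 16 subjects in each of the 1.2, 2.4 and 4.8 mg cohorts ("12 and 4 subjects in the DS-1040b and placebo groups, respectively") and 6 or 12 subjects, all on DS-1040b, at 0.6 mg. Its rationale says that the size and the two-event criterion follow Study U103. That study started from a 16% incidence of symptomatic intracranial hemorrhage (sICH) in rt-PA studies and chose "a sample size that allows the assessment of an incidence of symptomatic intracranial hemorrhage of" no more than 16%. Section 1.2.2 expects a similar incidence here and concludes that "it was considered appropriate to use the same sample size for each cohort in the present study as in Study DS1040-A-U103". U103 is also split 3:1 (1.2.1.6: "8 or 16 subjects for Cohorts 1 and 2), and are randomized to a DS-1040b or placebo group in a 3:1 ratio").

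Two rules apply to the DS-1040b group within a cohort (12.4.2). Two sICH events at 36 hours stop the study. One sICH event at 96 hours means that "subject enrollment will be temporarily discontinued and the necessary actions to be taken, including discontinuation of the study, will be considered". Events put down to external causes do not count in either sICH rule. At 0.6 mg, an event in the first 6 subjects of the kind that calls for such consideration means that "an additional 6 subjects will be enrolled to confirm the safety in a total of 12 subjects" (3.1). Section 12.3.3.1 plans point estimates and 95% confidence intervals by dose, with placebo pooled. Section 2.2 states that hypotheses do not apply.

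**The concern.** The only number offered in support of the cohort size is tied to 16 subjects, while both stopping rules and the by-dose intervals rest on 12, or on 6 at the lowest dose. The rationale does not define what assessing a rate of at most 16% means, and it gives no confidence level, precision or probability that a rule fires. A reader could take it that a completed cohort with few events shows the rate to be below 16%.

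That would matter because the primary objective is to confirm safety, and 12.5 says of the 0.6 mg cohort: "If DS-1040b at this dose is shown to be safe, the study will proceed to the next cohort". There is no data monitoring committee. The sponsor decides on escalation with a medical expert, so the sensitivity of the triggers carries weight.

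**Working it through.** **Plan's own figures.** 6 + 3 × 16 = 54 and 12 + 3 × 16 = 60, as stated. Treated per higher-dose cohort: 16 × 3/4 = 12, as stated. The statement about 16% cannot be reproduced, because 12.5 gives no criterion for it. The nearest match is a point estimate: 2/12 = 16.7%, the observed rate at which the study stops. The document does not say that this was the basis.

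**Inputs.** Treated n = 12, or 6 at 0.6 mg before any expansion (12.5). Stop at 2 events, pause at 1 (12.4.2). True rates p: 16% (12.5); 4.4% from the pooled thrombectomy trials (1.2.2: "patients also receiving thrombectomy device treatment was 4.3% and 4.4%, respectively"); and 4.9% (ICA) and 3.1% (M1) for endovascular treatment alone (1.2.2). The last two are closer to this trial, which excludes thrombolytics. The interval method is not named in 12.3.3.1; exact two-sided 95% limits are assumed.

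**Upper limits.** With no events the limit is 1 − 0.025^(1/n).
- 0/12: 1 − 0.7354 = 26.5% (Wilson: 24.2%)
- 0/6: 1 − 0.5407 = 45.9%
- 0/16, if all 16 counted: 1 − 0.7941 = 20.6%
- 1/12, from the beta quantile: 38.5%

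All exceed 16%. To put a two-sided limit at or below 16% with no events needs n ≥ ln(0.025)/ln(0.84) = 21.2, that is 22.

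**Trigger probabilities, n = 12.** Pause: 1 − (1−p)^12. Stop: 1 − (1−p)^12 − 12p(1−p)^11.

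| True rate | P(0 events) | P(1 event) | Pause | Stop |
|---|---|---|---|---|
| 3.1% | 0.6853 | 0.2631 | 31.5% | 5.2% |
| 4.4% | 0.5828 | 0.3219 | 41.7% | 9.5% |
| 4.9% | 0.5472 | 0.3383 | 45.3% | 11.4% |
| 16% | 0.1234 | 0.2821 | 87.7% | 59.5% |

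**0.6 mg cohort**, expanding from 6 to 12 after one sICH. Stop: 1 − [(1−p)^6 + 6p(1−p)^5 × (1−p)^6]. At 16% this is 1 − [0.3513 + 0.4015 × 0.3513] = 50.8%; at 4.4% it is 1 − [0.7634 + 0.2108 × 0.7634] = 7.6%.

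**Sensitivity.** If 10% or 20% of events were put down to external causes (an assumption), a 16% rate becomes 14.4% or 12.8%. The pause then falls to 84.5% or 80.7%, and the stop to 53.3% or 46.6%. Counting the pause to 96 hours instead of 36 pushes the other way, so the tabulated figures are bounds in neither direction.

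**The case for a change.** The strongest case for a change accepts that a phase 1 study need not be powered but holds that its rationale should say what its rules detect. At the protocol's own reference rate, about 4 in 10 cohorts of 12 (100% − 59.5% = 40.5%) would not meet the mandatory stop, so protection leans on a discretionary pause. At a harmless 4.4% in every cohort, with enrollment resuming after each pause, the mandatory stop would still fire somewhere in the study about 32% of the time: 1 − 0.9046³ × 0.9243 = 0.316. A sponsor without a monitoring committee would do well to know both. The later SAP would not help, because escalation decisions come before database lock.

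These figures stand, and so does the omission. They do not show a defect in what will be done. The sentence about 16% describes U103, whose derivation is not in these documents, and it promises no interval that excludes 16%. The remark about a dose being shown safe concerns 0.6 mg only. Escalation follows event counts, blinded adjudication and sponsor review with a medical expert, not a confidence limit. One event in 12 does not simply pass; it suspends enrollment. Subjects are also cleared for sICH one at a time until three aged 81 or over have been enrolled on DS-1040b (12.4.1).

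A supplementary row pooling all DS-1040b doses would be more precise, but it averages over an 8-fold dose range (4.8/0.6). A single event at 4.8 mg would read as 1/42 (upper limit 12.6%) against 1/12 (38.5%) at that dose. Reporting by dose is a fair choice in an escalation study.

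**Conclusion.** No change follows. The rationale is thin: it carries over U103's size and a 16% reference rate without saying what 12 or 6 treated subjects can show. But no stated number is wrong, the treated n and both thresholds are in the text, and a statistician can derive every operating characteristic from them, given an assumed rate. Adding those figures would leave the sample size, the rules, the by-dose intervals and the escalation decisions as they are. The by-dose 95% intervals will themselves show how little a small cohort excludes, up to 26.5% after 0/12 and 45.9% after 0/6.

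The trigger probabilities rest on one rate for both time windows, all events counted as not externally caused, full enrollment, and enrollment resuming after any pause. The limits rest on the exact method; the Wilson limit for 0/12 leads to the same conclusion.

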### **12.6 Statistical Analysis Process**

The clinical study will be analyzed by the sponsor or a designee/contract research organization (CRO).

The SAP will provide the statistical methods and definitions for the analysis of the efficacy and safety data, as well as describe the approaches to be taken for summarizing other clinical study information such as subject disposition, demographic and other baseline characteristics, study drug exposure, and prior and concomitant medications. The SAP will also include a description of how missing, unused, and spurious data will be addressed. To preserve the integrity of the statistical analysis and clinical study conclusions, the SAP will be finalized prior to database lock.

All statistical analyses will be performed using SAS® Version 9.2 or higher (SAS Institute, Cary, NC 27513).

## **13. DATA INTEGRITY AND QUALITY ASSURANCE**

The head of the study center and the investigator will provide direct access to all study-related documents, including source documents, at the implementation of monitoring and auditing by the sponsor as well as inspections by regulatory authorities and the IRB. The sponsor will have direct access to all study-related documents, including source documents, at the study center when performing monitoring and auditing to ensure appropriate implementation of the study and the reliability of the data. The sponsor will confer with the investigator in advance regarding procedures for source document verification.

### **13.1 Monitoring and Inspections**

The sponsor's and CRO's clinical research associates and the regulatory authority inspectors are responsible for contacting and visiting the investigator for the purpose of inspecting the facilities and, upon request, inspecting the various records of the study (eg, CRFs, source data, and other pertinent documents).

The verification of adherence to the protocol; completeness, accuracy, and consistency of the data; and adherence to the International Conference on Harmonization (ICH) Good Clinical Practice (GCP) and local regulations on the conduct of clinical research will be accomplished through the combination of onsite visits by the clinical research associate and remote review of study data. The frequency of the monitoring visit will vary based on the study progress at each study center. The clinical research associate is responsible for inspecting the CRFs and ensuring completeness of the study essential documents. The clinical research associate should have access to subject medical records and other study related records needed to verify the entries on the CRFs. Detailed information is provided in the monitoring plan.

The clinical research associate will communicate deviations from the protocol, SOPs, GCP and applicable regulations to the investigator and will ensure that appropriate action (s) designed to prevent recurrence of the detected deviations is taken and documented.

The investigator agrees to cooperate with the clinical research associate to ensure that any problems detected in the course of these monitoring visits are addressed to the satisfaction of the sponsor and documented.

In accordance with ICH GCP and the sponsor's audit plans, this study site may be selected for audit by representatives from the sponsor. Audit of study center facilities (eg, pharmacy, drug storage areas, laboratories) and review of study related records will occur in order to evaluate the study conduct and compliance with the protocol, ICH GCP, and applicable regulatory requirements. The investigator should respond to audit findings. In the event that a regulatory authority informs the investigator that it intends to conduct

an inspection, the sponsor must be notified immediately.

## 13.2 Data Collection

### 13.2.1 Preparation of the Case Report Form

A CRF must be completed by the investigator or subinvestigator for each subject who signs an ICF and undergoes any screening procedure. If a subject is not treated, the reason must be recorded on the CRF. All data collected during the study must be recorded in this individual, subject-specific CRF. Instructions will be provided for the completion of the CRF and any corrections made will be automatically documented via the electronic data capturing (EDC) software's "audit trail."

### 13.2.2 Precautions for Entering Data in the Case Report Form

The CRF (completed by the investigator), the Central Adjudication Form (prepared by the central adjudication committee member), the Drug Concentration Assay Data Report (prepared by the laboratory performing drug concentration assays), the Blood Coagulation Data Report (prepared by the laboratory performing blood coagulation assays), and the Biomarker Data Report (prepared by the laboratory performing biomarker assays) will be prepared in the study.

In this study, the CRF will be recorded using the EDC system (EDC System, Table 13.2-1), which is designed to electronically prepare CRFs. The CRF (including an audit trail) will be prepared for each subject and the one that was signed by the investigator will be handled as the original. A validated EDC system will be used in the study.

**Table 13.2-1 EDC System**

EDC system name	Medidata Rave®
EDC system development corporation	Medidata Solutions, Inc.
How to enter data	Data entry via the web interface
Terminal for data entry	PC at the study center
OS prohibited	None
Browser	Medidata Rave® supports any browser that conforms to HTML 5 and CSS2. JavaScript needs to be enabled in the browser.
Recommended screen resolution	1024 × 764 resolution or higher
Recommended connection speed	128 kbps or higher
Others	Adobe Flash Player ver. 10 or higher

